Appendix 3.3.2 Diagnosis versus Signs and Symptoms

For AEs, other than infusion-related reactions (see Section 3.3.1) a diagnosis (if known) should be recorded in the AE section of the eCRF rather than individual signs and symptoms (e.g., record only liver failure or hepatitis rather than jaundice, asterixis, and elevated transaminases). However, if a constellation of signs and/or symptoms cannot be medically characterized as a single diagnosis or syndrome at the time of reporting, each individual event should be recorded in the AE section of the eCRF. If a diagnosis is subsequently established, all previously reported AEs based on signs and symptoms should be nullified and replaced by one AE report based on the single diagnosis, with a starting date that corresponds to the starting date of the first symptom of the eventual diagnosis.

Appendix 3.3.3 Adverse Events Occurring Secondary to Other Events

In general, AEs that are secondary to other events (e.g., cascade events or clinical sequelae) should be identified by their primary cause, with the exception of severe or serious secondary events. A medically significant secondary AE that is separated in time from the initiating event should be recorded as an independent event in the AE section of the eCRF. For example:

- If vomiting results in mild dehydration with no additional treatment in a healthy adult, only vomiting should be reported on the eCRF.
- If vomiting results in severe dehydration, both events should be reported separately on the eCRF.
- If a severe gastrointestinal hemorrhage leads to renal failure, both events should be reported separately on the eCRF.
- If dizziness leads to a fall and subsequent fracture, all three events should be reported separately on the eCRF.
- If neutropenia is accompanied by an infection, both events should be reported separately on the eCRF.

All AEs should be recorded separately in the AE section of the eCRF if it is unclear as to whether the events are associated.

Appendix 3.3.4 Persistent or Recurrent Adverse Events

A persistent AE is one that extends continuously, without resolution, between patient evaluation time points. Such events should only be recorded once in the AE section of the eCRF. The initial severity (intensity or grade) of the event will be recorded at the time the event is first reported. If a persistent AE becomes more severe, the most extreme severity should also be recorded in the AE section of the eCRF. If the event becomes serious, it should be reported to Roche immediately (i.e., no more than 24 hours after learning that the event became serious; see Section 10.1.3.1 for reporting instructions). The AE section of the eCRF should be updated by changing the event from "non-serious" to "serious," providing the date that the event became serious, and completing all data fields related to SAEs.

A recurrent AE is one that resolves between patient evaluation time points and subsequently recurs. Each recurrence of an AE should be recorded separately in the AE section of the eCRF.

Appendix 3.3.5 Abnormal Laboratory Values

Not every laboratory abnormality qualifies as an AE. A laboratory test result must be reported as an AE if it meets any of the following criteria:

- · Is accompanied by clinical symptoms
- Results in a change in study treatment (e.g., dosage modification, treatment interruption, or treatment discontinuation)
- Results in a medical intervention (e.g., potassium supplementation for hypokalemia) or a change in concomitant therapy
- · Is clinically significant in the physician's judgment

It is the physician's responsibility to review all laboratory findings. Medical and scientific judgment should be exercised in deciding whether an isolated laboratory abnormality should be classified as an AE.

If a clinically significant laboratory abnormality is a sign of a disease or syndrome (e.g., alkaline phosphatase and bilirubin 5 ´ the upper limit of normal [ULN] associated with cholestasis), only the diagnosis (i.e., cholestasis) should be recorded in the AE section of the eCRF.

If a clinically significant laboratory abnormality is not a sign of a disease or syndrome, the abnormality itself should be recorded in the AE section of the eCRF, along with a descriptor indicating if the test result is above or below the normal range (e.g., "elevated potassium," as opposed to "abnormal potassium"). If the laboratory abnormality can be

characterized by a precise clinical term per standard definitions, the clinical term should be recorded as the AE. For example, an elevated serum potassium level of 7.0 mEq/L should be recorded as "hyperkalemia."

Observations of the same clinically significant laboratory abnormality from visit to visit should only be recorded once in the AE section of the eCRF (see Appendix 3.3.4 for details on recording persistent AEs).

Appendix 3.3.6 Abnormal Vital Sign Values

Not every vital sign abnormality qualifies as an AE. A vital sign result must be reported as an AE if it meets any of the following criteria:

- · Is accompanied by clinical symptoms
- Results in a change in study treatment (e.g., dosage modification, treatment interruption, or treatment discontinuation)
- Results in a medical intervention or a change in concomitant therapy
- Is clinically significant in the physician's judgment

It is the physician's responsibility to review all vital sign findings. Medical and scientific judgment should be exercised in deciding whether an isolated vital sign abnormality should be classified as an AE.

If a clinically significant vital sign abnormality is a sign of a disease or syndrome (e.g., high blood pressure), only the diagnosis (i.e., hypertension) should be recorded in the AE section of the eCRF.

Observations of the same clinically significant vital sign abnormality from visit to visit should only be recorded once in the AE section of the eCRF (see Appendix 3.3.4 for details on recording persistent AEs).

Appendix 3.3.7 Abnormal Liver Function Tests

The finding of an elevated ALT or AST (> 3 ´ the ULN) in combination with either an elevated total bilirubin (> 2 ´ the ULN) or clinical jaundice in the absence of cholestasis or other causes of hyperbilirubinemia is considered to be an indicator of severe liver injury. Therefore, physicians must report as an AE the occurrence of either of the following:

- Treatment-emergent ALT or AST > 3 $\acute{}$ ULN in combination with total bilirubin > 2 $\acute{}$ the ULN
- Treatment-emergent ALT or AST > 3 ´ ULN in combination with clinical jaundice

The most appropriate diagnosis or (if a diagnosis cannot be established) the abnormal laboratory values should be recorded in the AE section of the eCRF (see Appendix 3.3.5)

and reported to Roche immediately (i.e., no more than 24 hours after learning of the event) either as an SAE or a non-serious AE of special interest (see Section 10.1.3.1).

Appendix 3.3.8 Deaths

All deaths that occur during the protocol-specified AE reporting period (see Section 10.1.2.1), regardless of relationship to study medicine, must be recorded in the AE section of the eCRF and immediately reported to Roche (see Section 10.1.3.1).

Death should be considered an outcome and not a distinct event. The event or condition that caused or contributed to the fatal outcome should be recorded as the single medical concept on the AE section of the eCRF. Generally, only one such event should be reported. The term "sudden death" should only be used for the occurrence of an abrupt and unexpected death due to presumed cardiac causes in a patient with or without preexisting heart disease, within 1 hour after the onset of acute symptoms or, in the case of an unwitnessed death, within 24 hours after the patient was last seen alive and stable. If the cause of death is unknown and cannot be ascertained at the time of reporting, "unexplained death" should be recorded on the AE section of the eCRF. If the cause of death later becomes available (e.g., after autopsy), "unexplained death" should be replaced by the established cause of death.

Appendix 3.3.9 Preexisting Medical Conditions

A preexisting medical condition is one that is present at the screening visit for this study. Such conditions should be recorded on the General Medical History and Baseline Conditions in the eCRF.

A preexisting medical condition should be recorded as an AE only if the frequency, severity, or character of the condition worsens during the study. When recording such events in the AE section of the eCRF, it is important to convey the concept that the preexisting condition has changed by including applicable descriptors (e.g., "more frequent headaches").

Appendix 3.3.10 Lack of Therapeutic Efficacy

Events that are clearly consistent with the expected pattern of progression of the underlying disease should not be recorded as AEs. These data will be captured as effectiveness assessment data only. In most cases, the expected pattern of progression will be based on relapses and EDSS criteria. If there is any uncertainty as to whether an event is due to disease progression, it should be reported as an AE. This exception from reporting includes events of disease progression with a fatal outcome which are clearly attributable to disease progression.

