8.3 VARIABLES

8.3.1 Primary Safety Outcome Measures

The primary outcome measure for this study is as follows:

 incidence and type of uncommon AEs (i.e. AEs with an incidence rate of at least 0.1% [1 out of 1000 patients] at least once) and death with primary and underlying causes in patients with MS newly exposed to ocrelizumab

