- · Vital signs (BP, HR, body temperature) and weight
- Laboratory parameters, if available:
 - Blood cell count (RBC, hemoglobin, hematocrit, absolute and differential WBC, ANC, quantitative platelet count)
 - o Immunoglobuline levels (IgG, IgM, IgA)
 - o Liver enzymes (ALT, AST, gamma-GT
 - o Renal status (creatinine, BUN, urinalysis)
 - Clinical chemistry (alkaline phosphatase, amylase, total bilirubin, urea, uric acid, random glucose, potassium, sodium)
 - Flow cytometry (B-cell depletion and recovery [CD19+] and T-cell counts [CD3+, CD4+, CD8+])
- · Continuation of therapy or reason for discontinuation, if applicable
- Concomitant medications
- MS specific symptoms and treatment, relapses:
 - MS relapse during the treatment period (start/end dates)
 - Most recent EDSS score since the last encounter, if available
 - Most recent MRI results since the last encounter, if available
 - MS treatment changes and rationale

- Clinical management questions during study:
 - Gynecological consultation
 - o Breast check
 - Dermatological check
 - Malignancy/cancer detection tests (e.g., mammography, Pap test, colonoscopy, laboratory malignancy markers)
- Pregnancy status, if applicable (patient-reported, female patients)
- Safety assessments:
 - all AEs
 - SAEs
 - pregnancies
 - any malignancies, including but not limited to MedDRA Standardized MedDRA Queries (SMQ) of malignant or unspecified tumors, and non-melanoma skin cancers (NMSCs)
- Malignancy information, if applicable (questionnaire regarding in-depth malignancy information will be solicited from the patient's treating physician or oncologist [only collected if a malignancy is identified]), including, but not limited to:
 - Cancer type
 - Diagnosis date
 - Location of primary tumor
 - o Tumor grade
 - Stage at diagnosis
 - Action taken with ocrelizumab therapy at the point of diagnosis
 - AEs of special interest (AESIs):
 - Cases of potential medicine-induced liver injury that include an elevated ALT or AST in combination with either an elevated bilirubin or clinical jaundice, as defined by Hy's law (see Appendix 3).
 - Suspected transmission of an infectious agent by the study medicine (STIAMP)
 - Death information, if applicable (e.g., date of death, primary and underlying causes of death as entered for the AE)
- Ocrelizumab administration information (e.g., dates of administration [stop and restart dates, if applicable], dose, dosing frequency)
- QoL / PRO:
 - Clinical Global Impression (CGI)

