10.1.2.2 Procedures for Recording Adverse Events

Physicians should use correct medical terminology/concepts when recording AEs in the AE section of the eCRF. Colloquialisms and abbreviations should be avoided.

Only one AE term should be recorded in the event field of the eCRF.

See Appendix 3 for further specific instruction regarding:

- Infusion-Related Reactions
- Diagnosis versus signs and symptoms

- Adverse Events occurring secondary to other Adverse Events
- Persistent or recurrent Adverse Events
- Abnormal Laboratory Values
- Abnormal Vital Sign Values
- Abnormal Liver Function Tests
- Deaths
 - All events with an outcome or consequence of death should be classified as serious adverse events (SAEs) and reported to Roche immediately. In certain circumstances, however, suspected adverse reactions with fatal outcome may not be subject to expedited reporting. All deaths that occur during the protocol-specified AE reporting period, regardless of relationship to study medicine, must be recorded in the AE section of the eCRF and immediately reported to Roche
- Pre-existing Medical Conditions
- Lack of Therapeutic Efficacy
- Hospitalization or Prolonged Hospitalization
- Overdoses, Misuses, Abuses, Off-Label Use, Occupational Exposure, or Medication Error
- Drug Interactions
- Quality Defects and Falsified Medicinal Products

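### Appendix 3.3.10 exempts deaths from MS progression from AE recording while Appendix 3.3.8 and Section 10.1.2.2 require every death there, so the primary outcome can lose the cause of these deaths

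*Protocol*

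**What the plan says.** The primary outcome in Section 8.3.1 has two parts: uncommon AEs, "and death with primary and underlying causes in patients with MS newly exposed to ocrelizumab".

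Two places require every death to be recorded as an AE:
- Appendix 3.3.8 says that deaths in the AE reporting period, "regardless of relationship to study medicine, must be recorded in the AE section of the eCRF and immediately reported to Roche".
- Section 10.1.2.2 says: "All events with an outcome or consequence of death should be classified as serious adverse events (SAEs) and reported to Roche immediately".

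Appendix 3.3.10 gives a different instruction for one class of events: "Events that are clearly consistent with the expected pattern of progression of the underlying disease should not be recorded as AEs". It continues: "These data will be captured as effectiveness assessment data only". Its last sentence extends this to deaths: "This exception from reporting includes events of disease progression with a fatal outcome which are clearly attributable to disease progression".

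Section 8.4.2 lists death information among the safety assessments, with the date and the "primary and underlying causes of death as entered for the AE". Table 1 places the reasons for death in the AE row.

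**The concern.** The two sets of instructions give opposite answers for a death that the site attributes to MS progression. Neither appendix refers to the other, so a site has no rule for deciding which applies.

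What is at stake is a named component of the primary outcome. If the event is never entered as an AE, the death is missing from the AE/SAE-based count, and the field from which its causes would be read does not exist. The category that suffers is a single one, death from the underlying disease, so a cause-of-death table would be incomplete in one direction. The SAP cannot repair this, because it cannot tabulate causes that sites were told not to enter.

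**Working it through.** **Step 1. Follow one death through the protocol.** Take a patient whose death the physician attributes without doubt to MS progression.

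| Question | Under Appendix 3.3.8 and Section 10.1.2.2 | Under Appendix 3.3.10 |
|---|---|---|
| Entered on the AE page? | Yes, as an SAE | No |
| Where do the data go? | Safety data | Effectiveness data only |
| Is there a source for the cause (Section 8.4.2)? | Yes, the AE entry | None described |
| In the safety analysis of reported AEs and SAEs (Section 8.7.1)? | Yes | No |
| Taken up by an effectiveness outcome (Section 8.3.2)? | Not needed | No; none includes death |

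**Step 2. Look for text that reconciles the two.**
- Section 10.1.2.2 remarks that some fatal suspected reactions may escape expedited reporting. That concerns speed of reporting, not recording.
- Sections 8.4.4 and 10.1.1.2 list the events left to the effectiveness data, such as EDSS progression and disability. They do not separate fatal from non-fatal events.
- Appendix 3.3.10 opens by saying what is not to be recorded, so it cannot be read as a rule on reporting to the sponsor alone.

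No reconciling text was found.

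**Step 3. Look for other routes by which a death is captured.** The Table 1 footnotes give death as an example of a reason for early termination. Section 9.1.1 asks for an early termination visit when a patient dies. Section 8.7.1 plans disposition tables for all enrolled patients. These routes carry the fact of death. None of them describes a field for the primary and underlying cause.

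**Step 4. Size.** The protocol has no figure for expected deaths, so there is nothing to reproduce on this point directly. The nearest figures are those of Section 8.5, and they hold: n = −ln(0.05)/0.001 = 2995.7, stated as about 3000, and the Table 2 row for 30 events in 3000 gives a Clopper-Pearson interval of 0.68% to 1.42%. Neither is affected by this point.

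For illustration only, assume 30 deaths in 3000 patients and that a share s is withheld from the AE page. The AE-based count is then 30 × (1 − s):

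| Assumed share s | Deaths on AE page | Proportion | 95% CI |
|---|---|---|---|
| 0 | 30 | 1.00% | 0.68% to 1.42% |
| 10% | 27 | 0.90% | 0.59% to 1.31% |
| 25% | 22 (22.5 taken as 22) | 0.73% | 0.46% to 1.11% |
| 50% | 15 | 0.50% | 0.28% to 0.82% |

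The effect on the cause category is sharper. Deaths from MS progression could show as 0 of 3000 (upper limit 0.12%) when 3 to 15 had occurred (0.1% to 0.5%).

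The only evidence on cause in the protocol is Section 6.2: 2 + 1 + 1 + 4 = 8 deaths in the pivotal trials, none listed as MS progression. With 0 of 8, the upper 95% Clopper-Pearson limit for the share is 1 − 0.025^(1/8) = 0.37. This points to a low share but does not exclude a sizeable one, and the present study follows patients for far longer than the 96 weeks of the RMS trials.

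**The case against.** The strongest reply is that this is one badly worded sentence set against a repeated rule that all deaths are recorded. Death information is its own item in Section 8.4.2, so the intention to collect causes for every death is plain. The exemption is also narrow: Appendix 3.3.10 sends any uncertain case to the AE page, and Appendix 3.3.8 asks for the event that caused or contributed to the death. A fatal pneumonia in a disabled patient would therefore normally be entered as an AE.

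Much of this stands. It limits the exposed class to deaths that the site regards as plainly due to progression. It does not remove the conflict, because for that class the instruction not to record is explicit and the cause field depends on the AE entry.

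A reader might go further and infer that all-cause mortality will be under-counted by some stated percentage and cannot be recovered. The documents do not support that. Early-termination reasons, the termination visit and the disposition tables can yield a count of deaths, and data clarification (Section 8.6.1) or sponsor follow-up (Section 10.1.4.2) could recover some causes.

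A reader might also infer that the loss falls mainly on PPMS patients, or compare it with the 3 events implied by 3000 × 0.1%. The protocol gives no cause-of-death data that would place progression deaths in PPMS. The 3 events are the expected number for a single AE type at the detection threshold, not a figure for deaths.

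**Conclusion.** The protocol is wrong as written. Appendix 3.3.10 contradicts Appendix 3.3.8 and Section 10.1.2.2 for deaths that the site judges plainly due to MS progression. The firm consequence is limited to two things: the primary and underlying cause of those deaths, and the AE/SAE-based death count. Both bear on the primary outcome.

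All-cause mortality may be affected but need not be. The sample size, Table 2 and the malignancy, malignancy-mortality and serious-infection outcomes are untouched. The size of the loss is unknown: the figures under the assumed 30 deaths show only how the count would respond. The conclusion assumes that at least some sites would follow Appendix 3.3.10 as it reads, and that the eCRF ties cause of death to the AE entry, as Section 8.4.2 says.

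**What to change.** - **Appendix 3.3.10:** delete the last sentence, or limit the exemption to non-fatal events, and add a cross-reference to Appendix 3.3.8.
- **Sections 8.4.4 and 10.1.1.2:** state that every death, including death from MS progression, is recorded with date, primary cause and underlying cause, whether or not it is reported as an expedited SAE.
- **Analysis of death:** base it on that record, and check it against the early-termination reasons. Query any patient with death as the reason for termination and no recorded cause.

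The cost is a short amendment, a reminder to sites and a few additional death entries. The change goes beyond administrative matters, so Section 4 requires ethics committee approval, and approval by the authorities where locally required. No extra analysis is needed beyond the cross-check. With follow-up of up to 10 years, an early correction avoids having to establish causes long after the event.

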Appendix 3.3.11 Hospitalization or Prolonged Hospitalization

Any AE that results in hospitalization or prolonged hospitalization should be documented and reported as an SAE (per the definition of SAE in Section 10.1.1.2), except as outlined below.

The following hospitalization scenarios are not considered to be SAEs:

- Hospitalization for respite care
- Hospitalization for a preexisting condition, provided that all of the following criteria are met:
 - The hospitalization was planned prior to the study or was scheduled during the study when elective surgery became necessary because of the expected normal progression of the disease.
 - The patient has not suffered an AE.

Appendix 3.3.12 Overdoses, Misuses, Abuses, Off-Label Use, Occupational Exposure, or Medication Error

Any overdose, misuse, abuse, off-label use, occupational exposure, medication error (including intercepted or potential), or any other incorrect administration of medicine under observation should be noted in the Drug Administration section of the eCRF. Any overdose, misuse, abuse, off-label use, occupational exposure or medication error (including intercepted or potential) reports must be forwarded to Roche with or without an AE.

Reports with or without an AE should be forwarded to Roche as per non-serious timelines. If the associated AE fulfills the seriousness criteria, the event should be reported to Roche immediately (i.e., no more than 24 hours after learning of the event, see Section 10.1.3.1).

For the purpose of reporting cases of suspected adverse reactions, an occupational exposure to a medicine means an exposure to a medicine as a result of one's professional or non-professional occupation.

Appendix 3.3.13 Quality Defects and Falsified Medicinal Products

Reports of suspected or confirmed falsified medicinal product or quality defect of a medicinal product, with or without an associated AE, should be forwarded to Roche as per non-serious timelines. If the associated AE fulfills the seriousness criteria, the event should be reported to Roche immediately (i.e., no more than 24 hours after learning of the event, see Section 10.1.3.1).

